With 76 evaluable patients randomized between risedronate and rhIGF-I for the first six months, we will have an 80% chance of detecting a difference of 13 units in PINP. This represents a difference of 25% of the baseline value of PINP in patients with AN. For the difference between these groups (sequential therapy and risedronate) over the 12-month period, we will be able to detect a difference of 0.13 units in CTX at a 5% significance level. For CTX, the difference is 19% of the baseline level. The power calculation was based on a repeated measures analysis of covariance with the baseline value as a covariate and two post baseline measurements. We used the programs provided by [REDACTED] (92). The variance covariance matrix of the measurements were (350,360;360,535) for PINP and (0.05,0.012;0.012,0.049) for CTX and are from our pilot study with 36 patient completers in the risedronate only and double placebo groups.

Muscle mass

With 40 women in the rhIGF-1 group and 20 in the placebo group, the probability is 80% that the study will detect a treatment difference at a two-sided 5.0% significance level, if the true difference between the treatments is 4.3%. This is based on the assumption that the SD of the response variable is 5.2%, as we found when we examined the 6-month change from baseline in women of reproductive age receiving placebo (93). We conclude that this is feasible because it is smaller than the 6% change in fat-free mass that was produced by IGF-1 in our previously published study in patient with AN (24).

GH and IGF-1

With 40 women in the rhIGF-1 group and 20 in the placebo group, the probability is 80 percent that the study will detect a treatment difference at a two-sided 5.0% significance level, if the true difference between the treatments is 0.7 times the SD of change from baseline.

Bone microarchitecture: Spine

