The literature on trabecular thickness uses percent change as the unit of effect. With 36 evaluable patients in each treatment group the 95% confidence interval on the change in trabecular thickness of the spine will be 2.7% for each of the two active treatments based on Graeff *et al.* who estimated the difference between two spine microarchitectural endpoint measurements 12 months apart to be 8.8%, depending on the measure, and the SD of the change of 8.2% (73). Based on this we will be able to estimate trabecular thickness at the spine to sufficient precision to be confident as to whether the treatments affect this variable.

Radius and Tibia

With 40 patients in each treatment group and 20 in the placebo group entering the study and a 10% drop-out rate, the probability is 80 percent that the study will detect a treatment difference at a two-sided 5.0% significance level, if the true difference between the treatments is 2%. This assumes that the within subject SD is 3%, which is the interscan variation described for the instrument (94). If the within patient SD is twice this, e.g. 6%, we would be able to detect a change in trabecular thickness of 4%, which is smaller than the difference between women with and without fractures of 6% (95). In addition, for both of the comparisons with placebo, we will be able to detect a 2.5% difference between groups with an 80% probability. If the within patient SD is twice this, we would be able to detect a change in trabecular thickness of 5%. Thus, we think that this measurement has the potential of detecting small clinically important differences in this parameter. The SD of 6% is greater than the SD found in the EUROFORS study using similar high-resolution CT scanners after 6 months of treatment with PTH of 5.6% (73). In the powering, we focus on the pairwise comparisons of the treatment arms because the scientific questions are distinct for each pairwise comparison.

Bone strength (FEA)

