The literature on FEA standardizes measurements using the population SD standard deviation. We refer to one population SD as a unit. For strength, with 36 evaluable patients in each treatment group the 95% confidence interval of the change in FEA of the spine will be ± 0.33 units for each of the two active treatments. This is based on Graeff *et al.* who estimated the difference between two measurements 12 months apart to be 0.43 to 0.82 units, depending on the measure, and the SD of the change of one unit (73). Orwoll *et al.* demonstrated that 1 unit produces a hazard ratio of 3.196. Based on this, we will be able to estimate FEA to sufficient precision to be confident as to whether the treatments affect this variable.

Exploratory Aim

Sequential therapy with physiologic rhIGF-1 administration replacement followed by a bisphosphonate will increase spine bone strength in women with AN compared with bisphosphonate or placebo. We will develop a novel FEA model to determine spine strength using high resolution MDCT data. [REDACTED] has recently published the development and validation of such a model for wrist and leg strength in AN (78), and [REDACTED] is a world-renowned expert in this area (82,84,96) and will serve as a consultant on this project. For power and data analyses, please see sections on FEA of wrist above.

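### Spine thickness and spine FEA precision is stated per arm although the planned comparisons are between arms; for FEA the between-arm precision does not support the SAP's conclusion at the low end of its cited range

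*SAP*

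**What the plan says.** **Spine thickness** (SAP, power section, Bone microarchitecture: Spine). With 36 evaluable patients per treatment group, "the 95% confidence interval on the change in trabecular thickness of the spine will be 2.7% for each of the two active treatments". The inputs come from a cited study: a difference of 8.8% between two measurements 12 months apart, and an SD of change of 8.2%.

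**Spine FEA** (SAP, Bone strength (FEA)). Again with 36 per group, "the 95% confidence interval of the change in FEA of the spine will be ± 0.33 units for each of the two active treatments". The same cited study "estimated the difference between two measurements 12 months apart to be 0.43 to 0.82 units", with an SD of change of one unit.

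Both paragraphs end by saying that the precision is enough to be sure whether the treatments affect the measure. Neither gives a figure for the placebo arm or for a difference between arms.

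**Radius and tibia** (SAP, Radius and Tibia). This paragraph is framed between arms. It leads with 80% power for a 2% difference, and explains the input: "This assumes that the within subject SD is 3%, which is the interscan variation described for the instrument (94". Next comes a second case: "If the within patient SD is twice this, e.g. 6%, we would be able to detect a change in trabecular thickness of 4" percent. Against placebo, "for both of the comparisons with placebo, we will be able to detect a 2.5% difference between groups with an 80% probability", or 5% at the doubled SD. The larger SD is then defended: "The SD of 6% is greater than the SD found in the EUROFORS study using similar high-resolution CT scanners after 6 months of treatment", that SD being 5.6%.

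**The planned comparisons.** Protocol Specific Aim 2 and the SAP's Exploratory Aim set sequential therapy against bisphosphonate or placebo. The SAP's analysis section for bone microarchitecture and strength plans analyses of covariance at 6 and 12 months. The Radius and Tibia paragraph says that the powering is directed at pairwise comparisons of arms.

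**The concern.** A one-arm interval describes how well the mean change in that arm is known. It does not separate the treatment effect from whatever else changes over 12 months, which is why the trial has comparators. The interval for a difference carries the sampling error of both arms, and the placebo arm has half the patients.

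The issue is sharpest for FEA. The one-arm ±0.33 lies below the whole cited range of 0.43 to 0.82 units, so the precision looks sufficient. The between-arm half-widths may not lie below it. If they do not, a null FEA comparison could be read as showing no treatment difference when the design could not exclude differences of the size the SAP itself cites.

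The radius and tibia point is smaller. The first figures a reader meets rest on instrument variation, whereas the muscle mass section uses a response SD: "the SD of the response variable is 5.2%, as we found when we examined the 6-month change from baseline".

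**Working it through.** **Inputs, all from the SAP's power section.** 40:40:20 enter and 10% drop out, giving 36:36:18 evaluable. Tests are two-sided at 5%. SD of change is 8.2% for spine thickness and 1 unit for spine FEA. For radius and tibia the SD is 3% or 6%, with 5.6% cited from a treatment study.

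**1. The SAP's figures reproduce.**
- One-arm half-width = 1.96 × SD/√36. Thickness: 1.96 × 8.2/6 = 2.68%. FEA: 1.96 × 1/6 = 0.327 units. These match 2.7% and ±0.33.
- Radius and tibia, noncentral t: at SD 3%, power is 79.7% for 2% (36 vs 36) and 80.9% for 2.5% (36 vs 18). Doubling both SD and difference leaves power unchanged, so 4% and 5% at SD 6% also match.

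**2. Between-arm half-widths** = t(0.975, n1+n2−2) × SD × √(1/n1 + 1/n2), without baseline adjustment.
- 36 vs 36: √(1/36 + 1/36) = 0.2357; t with 70 df = 1.994.
- 36 vs 18: √(1/36 + 1/18) = 0.2887; t with 52 df = 2.007.

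| | SAP, one arm | 36 vs 36 | 36 vs 18 |
|---|---|---|---|
| Thickness | 2.7% | 1.994 × 8.2 × 0.2357 = 3.9% | 2.007 × 8.2 × 0.2887 = 4.8% |
| FEA (units) | 0.33 | 1.994 × 0.2357 = 0.47 | 2.007 × 0.2887 = 0.58 |

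The SAP's one-arm figures use 1.96. On that same basis the between-arm values are 3.8% and 4.6%, and 0.46 and 0.57 units, which are √2 = 1.41 and √3 = 1.73 times the one-arm values.

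**3. Differences detectable with 80% power** (noncentral t, noncentrality = difference / [SD × √(1/n1 + 1/n2)]).
- Thickness: 5.5% (36 vs 36) and 6.8% (36 vs 18).
- FEA: 0.67 and 0.82 units.

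**4. Power at the cited magnitudes.** These are changes between two measurements; treating them as differences between arms is an assumption made only for scale.

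| Difference | Noncentrality (36/36; 36/18) | Power |
|---|---|---|
| Thickness 8.8% | 4.55; 3.72 | 99%; 95% |
| FEA 0.43 units | 1.82; 1.49 | 44%; 31% |
| FEA 0.82 units | 3.48; 2.84 | 93%; 80% |

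**5. Radius and tibia if the SD of change is 5.6% to 6%** (an assumption about what those SDs are).
- Power for 2% (36 vs 36): 32% at 5.6%, 29% at 6%.
- Power for 2.5% (36 vs 18): 33% at 5.6%, 29% at 6%.
- At SD 6%, power for the SAP's own benchmark, the 6% difference between women with and without fractures, is 99% and 92%.

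**The case against.** **Nothing is miscalculated or hidden.** This stands in full. The one-arm intervals are correct and labelled as applying to each active treatment. A reader might infer an arithmetic error; the documents contain none here.

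**The precision sentence could mean change within each treatment.** That reading is possible, but it answers a question that neither Aim 2 nor the Exploratory Aim asks. One detail is fair to the SAP: its explicit contrast with risedronate and placebo is attached to the 6-month analysis, and the protocol schedules the L1 CT only at baseline and 12 months. The aims still make the 12-month spine question a between-arm one.

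**0.43 units cannot be rejected as a between-arm effect and then used as a yardstick.** This is right as a caution. The half-widths and detectable differences do not depend on it. The 44% and 31% are conditional and show scale only. At the upper value of 0.82 units, power is 93% and 80%.

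**Analysis of covariance may do better than unadjusted figures.** It may, if baseline predicts change. The documents give no correlation, so the gain cannot be computed.

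**The radius and tibia paragraph already covers the realistic case.** Largely so. A reader might infer that the trial really has about 30% power for these endpoints. The documents do not support that: the SAP never pairs 2% or 2.5% with an SD near 6%, it states 4% and 5% in the same paragraph, and it ties its clinical benchmark to the 4% figure. Nor can the cited 5.6%, observed under a different treatment (PTH), be confirmed as an SD of change. Only a labelling point is left.

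**Conclusion.** The point holds for spine thickness and spine FEA as an omission: the conclusion about precision is drawn from one-arm intervals, and the interval for the planned contrast is about 1.4 times (active vs active) to 1.7 times (vs placebo) as wide. The consequence differs by endpoint. Thickness remains adequate for a between-arm difference as large as 8.8%. For FEA, both between-arm half-widths (0.47 and 0.58 units) exceed 0.43, so the sufficiency claim does not hold at the low end of the range. For radius and tibia it is a matter of labelling.

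The figures assume the SAP's SDs of change, equal across arms, 36:36:18 evaluable patients, and no gain from baseline adjustment. A reader might go further and conclude that the trial is under-sized. The documents do not support that: these endpoints are secondary or exploratory, and the sample size was set on PA spine BMD.

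**What to change.** - **Spine thickness:** replace or supplement the one-arm 2.7% with between-arm 95% half-widths of about 3.9% (36 vs 36) and 4.8% (36 vs 18), and 80%-power detectable differences of about 5.5% and 6.8%.
- **Spine FEA:** do the same with 0.47 and 0.58 units, and limit the concluding sentence to between-arm differences of about 0.67 units (active vs active) and 0.82 units (vs placebo).
- **Both:** say that the cited 8.8% and 0.43 to 0.82 units are changes between two measurements. Add that the figures are unadjusted and that analysis of covariance may narrow them by an amount not yet known.
- **Radius and tibia:** label 2% and 2.5% as a best case reflecting instrument interscan variation only, and let the existing 4% and 5% at SD 6% serve as the working figures.

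The cost is SAP wording and less favourable stated precision for secondary and exploratory endpoints. Enrolment, the analyses and the primary sizing do not change.
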